## 11.7 “STARTING THE CONVERSATION” BRIEF DIETARY ASSESSMENT

**“Starting the Conversation” Brief Dietary Assessment (8-item)**

Over the past few months:			
1. How many times a week did you eat fast food meals or snacks?	 Less than 1 time	 1-3 times	 4 or more times
2. How many servings of fruit did you eat each day?	 5 or more	 3-4	 2 or less
3. How many servings of vegetable did you eat each day?	 5 or more	 3-4	 2 or less
4. How many regular sodas or glasses of sweet tea did you drink each day?	 Less than 1	 1-2	 3 or more
5. How many times a week did you eat beans (like pinto or black beans), chicken, or fish?	 3 or more times	 1-2 times	 Less than 1 time
6. How many times a week did you eat regular snack chips or crackers (not low-fat)?	 1 time or less	 2-3 times	 4 or more times
7. How many times a week did you eat desserts and other sweets (not the low-fat kind)?	 1 time or less	 2-3 times	 4 or more times
8. How much margarine, butter, or meat fat do you use to season vegetables or put on potatoes, bread, or corn?	 Very little	 Some	 A lot

**Scoring Key:** The left column indicates the most healthful dietary practices (scored 0); the center column indicates less healthful practices (scored 1); and the right column indicates the least healthful practices (Scored 2). Item scores are added to create a summary score (range 0-16), with lower scores reflecting more healthful diet.

## 11.8 APPS AND DEVICES QUESTIONNAIRE

## Apps and Devices Questionnaire (7-item)

Are you currently using any apps to help monitor your weight?	 Yes. If yes, please specify which one(s).  No
Do you currently have a body weight scale at home?	 Yes  No
Do you currently have a digital body weight scale (Wi-fi or Bluetooth enabled) that automatically connects with your smartphone?	 Yes  No
Are you currently using any apps to help you monitor your nutrition or diet?	 Yes. If yes, please specify which one(s).  No
Are you currently using any apps to help you monitor your physical activity or exercise?	 Yes. If yes, please specify which one(s).  No
Are you currently using any apps to track your health data , such as labs or imaging results?	 Yes. If yes, please specify which one(s).  No
Are you currently using any wearable fitness trackers?	 Yes. If yes, please specify which one(s).  No

## 11.9 NPART SURVEY

**NPART Survey (Adapted) (28-item\*)**

The NPART (Evaluation of Non-Participation in Digital Health Research) survey is a validated instrument to characterize non-participation in digital health research. The survey was developed and evaluated in an European population. We have adapted the questions for the U.S. setting. For the purposes of this trial, the results of this survey will not be used to exclude eligible participants. Rather, responses will be analyzed as predictors of responsive to digital vs. in-person DPPs.

What is your current employment status?	 1 Employed. _____ hours per week  0 Not employed, looking for work  0 Not employed, NOT looking for work  0 Retired  0 Disabled, not able to work
What is/was your primary job?*	
Which of the following categories best describes your primary area of employment?	 1 Manager  2 Professionals  3 Technicians and Associate Professionals  4 Clerical Support Workers  5 Services and Sales Workers  6 Skilled Agricultural, Forestry, and Fishery Workers  7 Craft and Related Trade Workers  8 Plants and Machine Operators, and Assemblers  9 Elementary Occupations  10 Armed Forces Occupations  11 I have never worked
Do you have a partner?*	 1 Yes  0 No
Do you live alone?*	 1 Yes  0 No
How often in the past 12 months did you care for a sick or disabled person?	 4 Almost daily  3 Almost every week  2 Almost every month  1 Less often
During the past 12 months, how often have you participated in social activities such as volunteer or charity work, attended a training course visited a sports club, social club or	 4 Almost daily

other kind of club, participated in the activities of a religious organization, or participated in the activities of a political or community-related organization?	 3 Almost every week  2 Almost every month  1 Less often
During the past 12 months, how often did you have contact with your children , either in-person, by phone, by mail, by e-mail or by other electronic means?	 5 Almost daily  4 Almost every week  3 Almost every month  2 Less often  1 I do not have any children
During the past 12 months, how often did you have contact with or meet with your friend and/or neighbors ?	 4 Almost daily  3 Almost every week  2 Almost every month  1 Less often
In the past 12 months, would you like to have had more contact with or met more frequently your children, relative, and/or friends?	 4 Much more  3 Little more  2 Not more  1 Less
How would you rate your memory at the present time? Would you say it is..	 5 Very good  4 Good  3 Fair  2 Bad  1 Very bad
How is your health in general? It is ...	 5 Very good  4 Good  3 Fair  2 Bad  1 Very bad
During the last 6 months, to what extent have you been limited because of your health in activities people usually do? Would you say you have been....	 3 Severely limited  2 Limited but not severely  1 Not limited at all
Do you require any help taking care of your health, such as taking medications or attending/booking appointments?	 4 Almost daily  3 Almost every week  2 Almost every month  1 Less often

How would you rate your quality of life?	 5	Very good
	 4	Good
	 3	Neither poor nor good
	 2	Poor
	 1	Very poor

\*NPART is 36 item questionnaire, but 8 questions appear on our demographics survey and will not be repeated.

**Now there are some questions regarding the use of the internet and technology.**

How well do you think you master the following activities?	Excellent	Good	Fair	Poor	Very Poor
Sending/receiving e-mails	 5	 4	 3	 2	 1
Buying goods or services over the Internet	 5	 4	 3	 2	 1
Reading or downloading online news, newspaper or magazines	 5	 4	 3	 2	 1
Internet banking	 5	 4	 3	 2	 1
Accessing institutions	 5	 4	 3	 2	 1
Playing or downloading games, images, films, or music	 5	 4	 3	 2	 1
Listening to web radio or watching web television	 5	 4	 3	 2	 1
Telephoning or making video calls over the Internet	 5	 4	 3	 2	 1
Social networking, for example Facebook or Twitter	 5	 4	 3	 2	 1
Posting messages to chat sites, blogs or forums, or instant messaging	 5	 4	 3	 2	 1

Do you think using a mobile phone, smartphone, tablet or the Internet might...	Yes	Maybe	No
Support you in performing everyday activities (e.g. remembering medications and appointments, calling for emergency)	 3	 2	 1
Be useful in monitoring your health (e.g. sleeping, diet, blood pressure, general symptoms)	 3	 2	 1
Be useful for contacting nurses, physicians, and other healthcare professionals	 3	 2	 1

Finally, we would like to ask you how often you use:	Daily	At least once per week	At least once per month	Less than once per month	Never
Computer	 5	 4	 3	 2	 1

Mobile phone	 5	 4	 3	 2	 1
Smartphone and/or tablet	 5	 4	 3	 2	 1
Smart television and/or games console	 5	 4	 3	 2	 1

## 11.10 ACCEPTABILITY QUESTIONNAIRE

## Acceptability Questionnaire (32-item)

[figure not shown]
Please rate your diabetes prevention program from strongly disagree to strongly agree to strongly agree:	Strongly disagree	Disagree	Neutral	Agree	Strongly agree
1. The [Sweetch DPP/ In-person DPP] gave me information and advice in an interesting way.	 1	 2	 3	 4	 5
2. I had fun using the [Sweetch DPP/ In-person DPP]	 1	 2	 3	 4	 5
3. The [Sweetch DPP / In-person DPP] motivated me to make lifestyle changes to prevent diabetes.	 1	 2	 3	 4	 5
4. The [Sweetch DPP/ In-person DPP] is appropriate for patients like me with pre-diabetes.	 1	 2	 3	 4	 5
5. I felt capable of meeting the expectations of the [Sweetch DPP/ In-person DPP]	 1	 2	 3	 4	 5
6. The [Sweetch DPP/ In-person DPP] helped me to become or stay active.	 1	 2	 3	 4	 5
7. The [Sweetch DPP/ In-person DPP] helped me to adhere to a healthy diet.	 1	 2	 3	 4	 5
8. The [Sweetch DPP/ In-person DPP] helped me to achieve or maintain a healthy body weight.	 1	 2	 3	 4	 5
9. The information collected by the [Sweetch DPP/ In-person DPP] would be useful for my doctor to see.	 1	 2	 3	 4	 5
10. The [Sweetch DPP/ In-person DPP] helped me to lower my risk of developing diabetes.	 1	 2	 3	 4	 5
11. The [Sweetch DPP/In-person DPP] provided me useful tools to succeed in preventing diabetes.	 1	 2	 3	 4	 5
12. The [Sweetch DPP/ In-person DPP] was easy to use with my daily routine.	 1	 2	 3	 4	 5
13. The instructions for the [Sweetch DPP/ In-person DPP] were helpful.	 1	 2	 3	 4	 5
14. Information from the [Sweetch DPP/ In-person DPP] was provided in a way I could understand.	 1	 2	 3	 4	 5
15. The [Sweetch DPP/In-person DPP] was frustrating.	 5	 4	 3	 2	 1
16. It was easy to move between the [Sweetch app screens / In-person DPP course materials or sessions].	 1	 2	 3	 4	 5

17. The [Sweetch DPP/ In-person DPP] did not have [functions/information] I thought it would.	 5	 4	 3	 2	 1
18. The [Sweetch DPP/In-person DPP] was convenient for me.	 1	 2	 3	 4	 5
19. The [Sweetch app/ In-person DPP course materials or sessions] were logically ordered .	 1	 2	 3	 4	 5
20. The [graphics and icons/ visual materials] were consistently high quality .	 1	 2	 3	 4	 5
21. I liked the way the [Sweetch app/ In-person DPP course materials] looked .	 1	 2	 3	 4	 5
22. The layout and appearance made the [Sweetch app/ In-person DPP course materials] easy to [navigate/follow] .	 1	 2	 3	 4	 5
23. I trusted the information from the [Sweetch app/In-person DPP] was accurate.	 1	 2	 3	 4	 5
24. The information provided by the [Sweetch app/ In-person DPP] was relevant to me.	 1	 2	 3	 4	 5
25. The [graphs and dashboards/ graphs and charts] made it easier to understand the information .	 1	 2	 3	 4	 5
26. I learned new things about prediabetes from the [Sweetch app/In-person DPP].	 1	 2	 3	 4	 5
27. I would like to keep using the [Sweetch DPP/ In-person DPP].	 1	 2	 3	 4	 5
28. I would recommend the [Sweetch DPP/In-person DPP] to people with prediabetes.	 1	 2	 3	 4	 5
29. I am satisfied with the [Sweetch DPP/In-person DPP].	 1	 2	 3	 4	 5
30. The good things about the [Sweetch DPP/In-person DPP] weren't worth how much effort I had to put in .	 5	 4	 3	 2	 1
31A. For dDPP arm only: I think I would have preferred an in-person diabetes prevention program over the digital version.	 5	 4	 3	 2	 1
31B. For hDPP arm only: I think I would have preferred a digital diabetes prevention program over the in-person version.	 5	 4	 3	 2	 1
32. Please provide any comments regarding your overall experiences with the [dDPP or in-person DPP]					

Scoring: Sum up all responses to questions 1-31, divide by 155 and multiply by 100 to calculate percentage score out of 100%. Range of possible scores is 20% (lowest acceptability) to 100% (highest possible acceptability).

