Acceptability (11.10)											x						x	
Sweetch App Features (dDPP only) (11.11)											x						x	
WHO-5 Well-Being Index (11.12)		x									x						x	
Healthcare Utilization (11.14)		x									x						x	
Monitoring of hDPP attendance and outcomes data entry (11.13)***											x						x	
Local DPP reimbursement (window is ±60 days)											x						x	
Adverse Event Evaluation (11.19)											x						x	
Participant reimbursement		x									x						x	
\$40 for study visit (mailed after home visits; provided during on-site visits)		x									x						x	
\$60 or \$70 for total Actigraph wear in months 1-6 (\$10 per each wear period)											x							
\$50 or \$60 for total Actigraph wear in months 7-12 (\$10 per each wear period)																	x	
Study End letter mailed to participant and primary care provider																	x	
Study End letter mailed/mailed to local DPP (hDPP arm)																	x	

En= enrollment;

\* For JHU site, study visits conducted at home or at clinical research unit per participant preference; for Reading site, all study visits conducted at clinical research unit.

\*\*Reminder 2 days prior to scheduled event and on day of event (or first business prior on or prior to event).

Study Procedures	En.	Days from Enrollment															
		-14 to 0	0	7	9	30	60	90	120	150	180	210	240	270	300	345	365
Study Window (days)			+ 4	-1 to +5	±14	±14	±14	±14	±14	±14	±14	±14	±14	±14	±14	±14	±14

\*\*\* Data from local DPPs will be entered into a RedCap database by the local DPP team. The research coordinator will validate the data entry and communicate with the local DPP as needed to correct any data entry errors or collect missing information.

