Considering this **access barrier**, it is not surprising that only a minuscule proportion of the eligible population is ever referred to a DPP. A recent study found that only 4.2% of eligible Medicare beneficiaries with prediabetes report having ever been referred to a DPP, and only 2.4% report ever participating. **Low referral rates** by healthcare professionals may be partly explained by their concerns about limited patient access to DPPs. Insufficient reimbursement rates by Medicare to cover the costs of the DPP has created a **health disparity** for low income populations.

Even among patients who are referred to DPPs, the unfortunate reality is that only about 35% actually attend the program. Several factors have been postulated to explain the **low rates of engagement** in DPPs, including low insurance reimbursement and patient competing priorities. Patients face several barriers in participating in hDPPs: travel distance, inconvenient hours,

costs, competing work/family demands, and lack of motivation. These obstacles are concerning because **engagement is an important mediator of success** in hDPPs: the magnitude of weight loss and PA correlate with the number and frequency of overall sessions attended and duration in the program. It appears that the main factors related to attrition are participants' perceptions of how likely they are to actually get diabetes, the effectiveness of behavioral change techniques, and program incentives.

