##### 5.6.2.2 LOCAL DPPS

Presently, some local DPPs participating in this trial seek reimbursement from insurance companies for the services they provide to their beneficiaries. **To encourage participation in the trial, we will cover all costs of the DPP for all study participants who are randomized to a local DPP.** We will implement contracts with each of the DPPs per participant enrolled in their program according to the current Medicare Diabetes Prevention Program Payment and Billing Guide at the time of completion of the participant's 6 and 12 month study visits. Reimbursements will be paid to the local DPPs at the 6 month and 12 month time points for each enrolled participant at their site. Since we will be collecting data from local DPPs as part of this study using an electronic data capture form (Section 11.13), we will compensate all local DPPs per participant referred to their program to cover the administrative expenses associated with data entry.

Local DPPs will receive payment once there data are marked "complete" for the participants record in an electronic data capture form and there are no validated data entry errors. The study coordinator will review data entry to identify any missing data or transcriptional errors and will contact the local DPP coordinator to resolve any data entry issues prior to dispensing payment. For participants who do not complete any local DPP visits, the DPP coordinator will simply mark the form "complete" and no data entry will imply that the participant did not engage in the program.

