Contracts will be established with each of the participating DPPs in the study to define expectations with respect to referral process, data entry, and billing procedures. Local DPPs will be asked to upload an invoice into the RedCap database system at the 6 month and 12 month time points, which will be reviewed by our study coordinators for payment verification. Payment will be sent within 30 days of receipt of the invoice. Reimbursement to the local DPPs will be based on attendance and outcomes data shared by the local DPP with the study team. A RedCap database will be created and DPPs will be asked to enter attendance and outcomes information for study participants into this database (see Section 11.13). The research coordinators will review the attendance and outcomes data to determine eligibility for payment, which will be assessed at the 6-month and 12 month time points. If the participant is inadvertently charged for any study-related expenses, including invoicing of their insurance company for their participation, we will reimburse the participant directly.

A total of \$75 will be paid for the 6-month data entry and \$75 for the 12-month data entry. Since there may be a lag between time from randomization in this trial and enrollment in the DPP, we will base the 6 month and 12 month time points on the time from initial local DPP visit for those participants who engage in the program; for participants who do not engage in the DPP (i.e. do not attend a single session), reimbursement will be based on the 6-month and 12-month *study visit* time points. In other words, if a participant completes their 12-month visit at a local DPP at time point 13 months on study, the local DPP will be expected to enter the attendance data (Section 11.13) received at time point 13 on study (12 month DPP program time point).

Data use agreements will be established with each of the participating DPPs in the study to define expectations with respect to data sharing, data entry, referral process, and study reimbursement.

	Core Sessions (Months 0-6)	Core Maintenance Sessions (Months 7-12)	
		Interval 1 (3 sessions)	Interval 2 (3 sessions)
Attendance Only	1 session total: \$26 (G9873) 4 sessions total: \$52 (G9874) 9 sessions total: \$94 (G9875)	Attend 2 sessions (without at least 5% weight loss): \$15 (G9876) OR	Attend 2 sessions (without at least 5% weight loss): \$15 (G9877)

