## 7 STUDY INTERVENTION DISCONTINUATION AND PARTICIPANT DISCONTINUATION/WITHDRAWAL

### 7.1 DISCONTINUATION OF STUDY INTERVENTION

Given the focus of this study on increasing PA and promoting healthy diet and weight loss, we do not anticipate any serious adverse events that would require discontinuation of the study intervention. For participants who do not engage with the study intervention, whether randomized to the dDPP or hDPP, all efforts will be undertaken by the research coordinator to keep the participant in the study for assessment of efficacy and adverse events.

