#### 9.4.8 ANALYSIS OF THE SECONDARY ENDPOINT(S)

Secondary endpoints will also be analyzed according to the ITT principle. Each of the individual outcomes in the CDC's benchmark for type 2 diabetes risk reduction (a composite endpoint) will be analyzed as a secondary endpoint at both the 6- and 12-month time points. As with the primary effectiveness endpoint, each outcome will be analyzed using logistic regression models. In addition, we will analyze change in A1C, absolute weight change and percentage weight change as continuous measures using linear regression models. Various physical activity measures will be analyzed as continuous measures, including average minutes/week of PA (light, moderate, intense), MET-hours per week of PA, and average number of steps per day. For responses from acceptability questionnaire (Likert-scale questions), non-parametric tests such as Spearman's correlation or chi-square test for independence will be used. For overall Likert scale scores, parametric tests such as Pearson's correlation or t-test will be used.

We anticipate that there will be a very low amount of missing data for the outcomes of A1C and weight for study completers, since both measures are collected by the research coordinator at the study visits. However, since the outcome of PA measurement relies on participants to wear the ActiGraph devices at 1-month intervals, there may be more missing data for this outcome variable. If more than 5% of data for this outcome variable is missing, the primary analysis will be based on multiple imputation. A sensitivity analysis will also be done using a complete case analysis (i.e. participants with 100% of valid PA data) and if results differ significantly, the primary analysis will be interpreted in light of results from the sensitivity analysis.

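### The acceptability and app-features scores divide by a fixed total and have no rule for blank items or for people who never used the programme, so the arm comparison of acceptability can partly reflect uptake

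*Combined protocol and SAP*

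**What the plan says.** **Scoring.** Section 11.10 gives the rule: "Sum up all responses to questions 1-31, divide by 155 and multiply by 100 to calculate percentage score out of 100". It adds: "Range of possible scores is 20% (lowest acceptability) to 100% (highest possible acceptability". Section 11.11 (app features, dDPP arm only) sums items 1 to 21 over 105 and states the same 20% to 100% range. Every item has five response levels. Neither form has a not-applicable or did-not-use option.

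**Who receives the forms.** The schedule in Section 1.3 lists the acceptability form at 6 and 12 months without restricting it to users. The next row, for the app-features form, is restricted to the dDPP arm.

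**Non-users remain in the study.** Section 7.1 says that staff will try to keep these people in follow-up: "For participants who do not engage with the study intervention, whether randomized to the dDPP or hDPP". Section 5.6.2.2 has a procedure for hDPP participants with no visits: "For participants who do not complete any local DPP visits, the DPP coordinator will simply mark the form" as complete.

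**Analysis.** Section 9.4.8 states: "Secondary endpoints will also be analyzed according to the ITT principle". It names parametric tests such as the t-test for overall Likert scores and separate tests for the individual Likert responses.

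**Missing questionnaire data.** Section 8.2.5 has incomplete responses chased by phone or at the visit. The multiple-imputation rule in 9.4.2, repeated in 9.4.8, concerns physical activity data only. No section says how a remaining blank is scored, or whether a never-user is scored, treated as missing or left out.

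**The concern.** Acceptability is a secondary endpoint, and Section 3.1.2 hypothesises in advance that the dDPP will be rated higher. Two gaps affect it.

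First, the score treats an unanswered item as worse than the lowest answer on the scale. Two people with the same opinion get different scores if one leaves items blank.

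Second, many items presuppose exposure: whether the programme was fun, whether screens or sessions were easy to move between, whether the graphics were good. Someone who attended no session or never installed the app cannot answer these meaningfully, and the form gives no way to say so. Whatever that person enters goes into an ITT mean. If non-start differs between arms, part of the acceptability difference measures uptake, which the protocol already reports through engagement and completion.

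Because the plan is silent, the handling would be chosen after data are seen, in a trial whose biostatistician is unmasked to assignment (Section 6.4).

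**Working it through.** **1. Reproduce the stated range (11.10).** Inputs: 31 items scored 1 to 5, divisor 155.
- Maximum: 31 x 5 / 155 = 100%.
- Minimum: 31 x 1 / 155 = 20%.

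The range reproduces, but only for a form with all 31 items answered. For 11.11, 21 x 5 / 105 = 100% and 21 x 1 / 105 = 20%, on the same condition.

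**2. Effect of blanks, formula applied literally.** With mean answer m and k blanks, the score is 100 x m x (31 - k) / 155. The mean of answered items x 20 gives 20m whatever k is.

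| Blanks (m = 4) | Sum / 155 | Mean of answered x 20 |
|---|---|---|
| 0 | 80.0% | 80% |
| 1 | 77.4% | 80% |
| 3 | 72.3% | 80% |
| 5 | 67.1% | 80% |
| 10 | 54.2% | 80% |

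- One skipped item worth 4 (Agree on a positively worded item) costs 4 / 155 = 2.6 points in 11.10 and 4 / 105 = 3.8 points in 11.11.
- Across possible answers, one blank in 11.10 costs from 1 / 155 = 0.6 to 5 / 155 = 3.2 points.
- Floor: a respondent scoring 1 on every answered item falls below 20% with one blank (30 / 155 = 19.4%). One scoring 5 on every answered item does so at 25 blanks (6 x 5 / 155 = 19.4%).

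**3. Never-users.** Neutral on every item gives 31 x 3 / 155 = 60%, the scale midpoint.

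Let u be the proportion of an arm that never starts. Assume users in both arms rate 75% and non-starters answer Neutral throughout. The arm mean is 75 x (1 - u) + 60 x u, so the arm difference is 15 x (difference in u). Take u = 10% in dDPP, giving 75 x 0.90 + 60 x 0.10 = 73.5.

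| hDPP never started | hDPP mean | dDPP minus hDPP |
|---|---|---|
| 10% | 73.5 | 0 |
| 20% | 72.0 | 1.5 |
| 30% | 70.5 | 3.0 |
| 50% | 67.5 | 6.0 |

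Users' opinions are identical in every row. If non-start were higher in the dDPP arm, the sign would reverse. All inputs in this step are assumptions; the protocol gives no expected uptake by arm.

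**The case against.** The strongest reply is that the stated 20% to 100% range shows the formula was written for a complete form. On that view a blank form is simply a missing questionnaire, and Section 8.2.5 already chases incomplete responses, helped by the missing-data checks described in 10.1.11.1. Much of this stands. Follow-up will reduce blanks, and counting a blank as 0 is the literal result of the formula rather than a declared rule. But follow-up gives no rule for what remains, and it cannot make an inapplicable item answerable.

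A reader might infer three stronger things that the documents do not support.

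- *Never-users receive a low or zero score.* Nothing fixes their score. It could be missing, or 60% if they answer Neutral. Differences computed with non-starters at 0 would rest on a rule that the plan does not state.
- *The comparison is biased towards the dDPP.* That needs non-starters to be scored and non-start to be higher in the hDPP arm. With equal non-start, or with non-starters left out, the illustration gives 0. App users also have a step to complete, since they must download and register, and both arms allow up to five outreach attempts (6.1, 6.2).
- *Non-start will be common.* Section 2.2 says that among referred patients "only about 35% actually attend the program", but this is background on referral to such programmes. Here participants agree to comply and to be randomised (5.1, 5.2), the study pays all hDPP costs (5.6.2.2), and randomisation pauses unless a class can start within four weeks (6.4).

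It is also fair to say that excluding never-starters outright would be a poor remedy. It conditions on a post-randomisation event, and such people can still answer items on convenience (18), fit with routine (12) or preference (31). The individual-item tests in 9.4.8 do not depend on the divisor.

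**Conclusion.** The point holds as a specification gap in a secondary endpoint. The fixed-divisor score is correct only for complete forms; any item left blank after follow-up costs 0.6 to 3.2 points in 11.10 if the formula is applied as written, and can take the result outside the plan's own range. Without a did-not-use response or a rule for never-users, the acceptability contrast can partly reflect uptake. The illustrated size is 3 points for 10% against 30% non-start, assuming 75% among users in both arms and Neutral answers from non-starters. The documents establish neither that such a difference will occur nor its direction. The primary endpoint, the margin and the sample size are untouched.

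**What to change.** 1. In 11.10 and 11.11, replace the sum over 155 or 105 with the mean of answered items x 20. Set a minimum completion below which the score is missing; 80% is a reasonable example (at least 25 of 31 and 17 of 21 items), though it has no source in the protocol.
2. Add a did-not-use / not-applicable response to both forms, and state that it counts as unanswered for scoring.
3. In 9.4.8, report by arm the proportion who never started (no session in the attendance records, no installation in the app logs) beside the acceptability score.
4. Present the all-respondent ITT score together with a supplementary score among starters, labelled as not a fully randomised comparison.

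The cost is a survey edit, a few lines in 11.10, 11.11 and 9.4.8, and slightly more analysis. The attendance and app data are already collected. One consequence should be accepted openly: many never-starters will fall below the completion threshold and become missing, so the never-started proportions must be read with the score.
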